7.6 Reporting Adverse Events

The PI should instruct all subjects/caregivers on the procedure for reporting AEs/SAEs to the appropriate clinical site personnel. For each AE reported by parents/guardians, clinical site personnel should obtain all required information to complete the eCRF.

The PI or designee should document all AEs/SAEs in subjects' source documentation and on the AE eCRF.

In addition to standardized reporting procedures, worsening or exacerbation of concurrent conditions in subjects will also be reported as AEs, and will follow the designated reporting format.

The following should be recorded with each SAE/AE:

- The nature of the AE, with a diagnosis wherever possible
- Date of event
- Assessment of intensity
- Is this an SAE?
- Relationship to study drug or trial-related procedures
- Action taken regarding study drug treatment
- Outcome

If the intensity of an already reported AE increases, then a new AE eCRF must be completed for that AE. The date of change would be included as the end date for the originally reported AE, and the start date for the new AE of greater intensity.

The clinical research associate is responsible for source document verification of all safety events.

If the clinical site becomes aware of an SAE, regardless of causality, within 30 days following the last administration of investigational product, the SAE should be recorded and reported immediately to the Sponsor. An SAE that occurs more than 30 days after the last dose will NOT be collected unless the PI considers that the event is related to the investigational product.

The sponsor should be informed if the PI becomes aware of any unusual safety information or any potential drug-related safety information, even after a subject completes the study

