6.1.22 Early Treatment Discontinuation and Follow-up

If for any reason, the investigator, subject or caregiver decide to discontinue the study drug or withdraw consent from the study, the subject and caregiver should be encouraged to complete an early termination (ET) visit and follow-up visit(s) as below:

- ET visit:
 - If the subject is withdrawn from the study at or before Week 13, subject will not enter Treatment Period 2.
 - If possible, schedule ET visits for 30 days (+/-2 days) after the last study drug dose administration
 - The ET reason must be documented with as much detail as possible in the EDC and in the source documents.

CONFIDENTIAL

- Follow-up Visits: Despite discontinuation of the study drug dosing, subjects and caregivers should be encouraged to return for additional follow-up visits for the duration of the trial, in order to monitor for safety and any changes in cognition.
 - The follow-up visits should be scheduled to coincide with the cognitive assessment visits scheduled after the study drug discontinuation (i.e., weeks 5, 9, 13, 15, 20, 24, 28, 30).
 - The below assessments should be completed at all follow-up visits:
 - SIB
 - Vitals
 - Adverse Events
 - Concomitant medications
 - If the subject is willing to return for only one follow-up visit, please schedule this visit to occur approximately 30 days (+/-2 days) following the last study drug dosing.

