7 ADVERSE EVENTS AND OTHER SAFETY EVALUATIONS

7.0 Definition of Adverse Events

An AE is any untoward medical occurrence associated with the use of a drug in humans, whether or not considered drug related. An AE (also referred to as an adverse experience) can be any unfavorable and unintended sign (e.g., clinically significant abnormal laboratory finding), symptom, or disease temporally associated with the use of a drug, without any judgment about causality.

The PI is responsible for obtaining information about all medical emergencies during the clinical study. The PI's contact information will be located in the body of the informed consent form (ICF) and subjects/caregivers will be encouraged to contact the PI or clinical site personnel during any clinical study-related emergency.

All adverse events spontaneously reported by the subject and/or caregiver in response to an open question or revealed by observation will be recorded during the study regardless of relationship to the study drug. All AEs will be monitored and recorded for the progress of the event until it resolves or reaches a clinically stable outcome. Adverse events that are not resolved at the time of database lock will be recorded as ongoing.

The AE and SAE reporting period starts from the time of consent to the last study visit.

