7.6.1 SAE reports

All SAEs, whether or not considered associated with study treatment or study-related procedures, must be reported on the eCRF immediately and no later than 24 hours after the site becomes aware of the event. Follow-up information must be provided promptly as requested.

CONFIDENTIAL

The PI is obligated to provide as much information about the event as possible on the eCRF provided and as requested by the Sponsor or Medical Monitor.

In general, this will include a description of the SAE in sufficient detail to allow for a complete medical assessment of the case. The pharmacovigilance physician or designee will review the SAE including the SAE criteria, the relationship to study medication, the expected or unexpected assessment, and inform the Sponsor by phone and e-mail immediately.

The following AEs should also be reported to the Sponsor's designated Medical Monitor immediately:

- severe injection/infusion site reactions (ulceration or necrosis that is severe; operative intervention indicated)
- systemic hypersensitivity reactions
- myalgia

All additional follow-up evaluations must be reported by the site to the medical monitor, or designee, immediately after notification of the additional information.

An SAE will be followed until it resolves or reaches a clinically stable outcome. AEs/SAEs that have not resolved by study closure will be considered ongoing.

An SAE that occurs after the 30-day safety visit will NOT be collected unless the PI determines that the event is related to the investigational drug product.

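### Protocol 7.0 conflicts with 7.6 and 7.6.1 on how long SAEs are collected in subjects who stop drug early but stay in follow-up to Week 30

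*Protocol*

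**What the plan says.** Two statements point to full collection:

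- Protocol 7.0: "The AE and SAE reporting period starts from the time of consent to the last study visit".
- Protocol 7.6.1, opening: "All SAEs, whether or not considered associated with study treatment or study-related procedures, must be reported on the eCRF immediately".

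Two point the other way:

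- Protocol 7.6: "An SAE that occurs more than 30 days after the last dose will NOT be collected". The one exception is an event that the PI attributes to study drug.
- Protocol 7.6.1, closing: "An SAE that occurs after the 30-day safety visit will NOT be collected unless the PI determines that the event is related".

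Section 6.1.22 governs subjects who stop study drug. It says "subjects and caregivers should be encouraged to return for additional follow-up visits for the duration of the trial", and gives the purpose as "in order to monitor for safety and any changes in cognition". The visits coincide with the remaining cognitive visits up to Week 30, and adverse events are on the list of assessments at each one. Section 5.6 similarly keeps a subject under safety and efficacy monitoring after unblinding has ended study drug.

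Treatment-emergent events (Protocol 9.8.1, SAP 6.12.1) are those starting on or after the first randomized treatment. Neither document gives an end date. No section says which SAE window takes precedence.

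**The concern.** Safety is part of the primary objective (Protocol 3.0), and the SAP tabulates serious treatment-emergent events by arm. A subject who stops drug in the first course and stays in follow-up can be seen for months after the 30-day limit. At those visits a site following 7.0 and the opening of 7.6.1 would report an unrelated hospitalisation as an SAE. A site following 7.6 or the end of 7.6.1 would not. Because the treatment-emergent definition is open-ended, both kinds of record would enter the same serious-event tables. The counts would then depend partly on which section each site read and on each PI's judgement of relatedness. They would also cover less follow-up time for some early discontinuers than for others.

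**Working it through.** The plan gives no figure to reproduce. The check is date arithmetic on the visit schedule, followed by a look at the earlier studies.

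**Inputs.** Dose and visit days come from Protocol 6.1.2 to 6.1.19: dose 1 on Day 0, dose 4 on Day 35, dose 7 on Day 77, dose 10 on Day 126, dose 13 on Day 168, dose 14 on Day 182, last visit on Day 210. Follow-up visits after stopping (6.1.22) fall at Weeks 5, 9, 13, 15, 20, 24, 28 and 30.

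**Formula.** Cut-off under 7.6 = day of last dose + 30. Conflict period = max(0, 210 − cut-off).

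| Last dose received | Day | Cut-off (day) | Conflict to Day 210 (days) | Follow-up visits after cut-off (weeks) |
|---|---|---|---|---|
| 1 | 0 | 30 | 180 | 5, 9, 13, 15, 20, 24, 28, 30 |
| 4 | 35 | 65 | 145 | 13, 15, 20, 24, 28, 30 |
| 7 | 77 | 107 | 103 (14.7 weeks) | 20, 24, 28, 30 |
| 10 | 126 | 156 | 54 | 24, 28, 30 |
| 13 | 168 | 198 | 12 | 30 |
| 14 (completer) | 182 | 212 | 0 | none |

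For completers the ±2-day windows could open a gap of at most 2 days: dose 14 on Day 180 closes on Day 210, and the last visit could be on Day 212. The limit in 7.6.1 is tied to the 30-day visit, not to 30 days after the last dose, so it can differ from 7.6 by a few days. That does not change the picture.

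**How much would the relatedness exception recover?**

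- Study 203 (Protocol 2.1.1.3): 15 SAEs, all rated unlikely related.
- Study 202 (Protocol 2.1.2.3): 14 non-fatal SAEs plus 1 death = 15. Four were rated possibly or probably related, all in the 40 µg arm. The death was rated unrelated.
- Together: (15 + 15 − 4) / 30 = 26/30 = 87% not reported as related.
- 20 µg and placebo arms only: 15 + 4 + 2 = 21 SAEs, none reported as related.

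**How many subjects could be exposed?** The ceiling is the number who receive drug and stop early.

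- Study 203 (2.1.1.2): 53 + 55 = 108 treated and 48 + 48 = 96 completed, so 12/108 = 11%.
- Study 202 (2.1.2.2): 35 of 141 treated withdrew early = 25%. This includes the 40 µg arm, which is not used here.
- Planning drop-out (Protocol 9.0): 20%.

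So the ceiling is roughly 11 to 25 per 100 subjects. Both earlier studies had a single 12-week course, so neither rate carries over directly.

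**Illustrative number of events.** Assume study 203's SAE rate over about 15 weeks: 15 / (108 × 15) = 0.0093 per subject-week. Assume also that every early stopper stops after dose 7 and attends to Week 30. The SAEs falling in the conflict period would then be 11 × 14.7 × 0.0093 = 1.5 at the low end and 25 × 14.7 × 0.0093 = 3.4 at the high end. Partial attendance lowers these figures; earlier stopping raises them.

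**The case against.** The strongest reply is that the protocol leans towards collection. Besides 7.0 and the opening of 7.6.1, section 7.6 itself asks the PI to document all AEs and SAEs in source and on the AE form, and that form records whether the event is serious. The adverse-event item in 6.1.22 is not limited to non-serious events. A careful site could well report everything. This stands: the documents show conflicting rules, not that SAEs will be lost. It does not remove the conflict, because 7.6 and 7.6.1 each contain an explicit instruction not to collect.

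One could also read the last study visit as the 30-day early-termination visit. That reading fails for subjects who continue, since 6.1.22 schedules further visits with adverse-event assessment.

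Three stronger inferences are tempting, and the documents do not support them.

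- *That all non-completers are affected.* The conflict reaches only treated subjects who stop early and attend beyond 30 days. Attendance is encouraged, not required, and a subject willing to make only one visit is booked at about 30 days. Many non-completers withdraw consent: in study 203, 8 of the 15 were subject withdrawals (5 + 3), and 3 of the 111 randomized were never dosed.
- *That the arm comparison is biased.* This needs stopping, or attendance after stopping, to differ by arm. In study 203 non-completion was 7/55 against 8/56. Safety is also summarised descriptively, with no formal tests (Protocol 9.3).
- *That deaths would go unrecorded.* SAP 6.12.1 refers to an End of Study page giving the reason for termination, SAP 6.4 tabulates withdrawal reasons, and the SAP plans a listing of fatal events. Study 203 captured death as a reason for termination.

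Finally, a 30-day limit on unrelated SAEs is a defensible choice in itself. The fault is that it sits beside an incompatible rule and beside follow-up set up to monitor safety.

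**Conclusion.** The contradiction is real and should be resolved. It is immaterial for completers on the current schedule. For early discontinuers who remain in follow-up it lasts from 12 days (last dose 13) to 180 days (last dose 1). In that time an SAE judged unrelated is required by one section and refused by another. If the earlier studies are a guide, nearly all SAEs at this dose and on placebo would be judged unrelated, so the exception offers little protection.

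The number of subjects affected is a minority and cannot be fixed from the documents. The ceiling of about 11 to 25 per 100 rests on shorter studies and a planning assumption, and voluntary follow-up and withdrawn consent bring the true figure below whatever the ceiling proves to be. The illustrative count is about 1.5 to 3.4 events if all stay. Differential bias by arm is a possibility, not a finding. The point warrants correction for consistent safety ascertainment; it does not undermine the trial.

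**What to change.** Reconcile 7.6 and 7.6.1 with 7.0 in one statement:

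- Collect all SAEs, whatever their relationship to study drug, through each subject's last attended study visit. Say explicitly that this includes follow-up visits after discontinuation (6.1.22) and monitoring after unblinding (5.6).
- Apply the related-only limit only to events after both that visit and 30 days from the last dose, so that no subject gets a shorter window than now.
- Word the rule by date of onset. At present one sentence in 7.6 turns on when the site becomes aware of the event and the next on when it occurs. An SAE that occurs within 30 days but is learned of later falls under neither.
- State in the SAP which period the serious-event tables cover.

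The cost is protocol and SAP wording and a few additional SAE reports. No visits or assessments are added. If the sponsor prefers the 30-day limit, 7.0 and the opening of 7.6.1 would have to change instead, and the serious-event tables should be cut at the same limit for every subject. That also removes the contradiction, but it gives up serious events that the follow-up visits are in place to detect.

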7.6.1 SAE reports

All SAEs, whether or not considered associated with study treatment or study-related procedures, must be reported on the eCRF immediately and no later than 24 hours after the site becomes aware of the event. Follow-up information must be provided promptly as requested.

CONFIDENTIAL

The PI is obligated to provide as much information about the event as possible on the eCRF provided and as requested by the Sponsor or Medical Monitor.

In general, this will include a description of the SAE in sufficient detail to allow for a complete medical assessment of the case. The pharmacovigilance physician or designee will review the SAE including the SAE criteria, the relationship to study medication, the expected or unexpected assessment, and inform the Sponsor by phone and e-mail immediately.

The following AEs should also be reported to the Sponsor's designated Medical Monitor immediately:

- severe injection/infusion site reactions (ulceration or necrosis that is severe; operative intervention indicated)
- systemic hypersensitivity reactions
- myalgia

All additional follow-up evaluations must be reported by the site to the medical monitor, or designee, immediately after notification of the additional information.

An SAE will be followed until it resolves or reaches a clinically stable outcome. AEs/SAEs that have not resolved by study closure will be considered ongoing.

An SAE that occurs after the 30-day safety visit will NOT be collected unless the PI determines that the event is related to the investigational drug product.

7.6.2 Reporting to Regulatory Authorities

The PI, or designee, is responsible for informing the Institutional Review Board (IRB) of any unexpected SAEs, as well as any additional SAEs according to the IRB's policy.

Any SAE that is serious, suspected to be related to investigational study drug and unexpected (SUSAR), will be promptly reported to regulatory authorities by the Sponsor according to expedited reporting requirements. Subsequent relevant information after the initial submission of the (IND) Safety Report to the regulatory authorities will be submitted in a follow-up IND Safety Report to the regulatory authorities in the expedited period by the Sponsor.

7.7 Criteria for Withdrawal of Subjects

Subjects may be withdrawn from the clinical study for the following reasons:

- The PI believes withdrawal to be medically necessary or in the best interest of the subject
- Noncompliance with the protocol as judged by the PI (requires discussion with the Sponsor)
- Subjects who are enrolled in violation of inclusion and/or exclusion criteria
- An AE that presents an unacceptable consequence or risk to the subject as judged by the PI, Sponsor or the Medical Monitor
- Lost to follow up
- Withdrawal of consent

CONFIDENTIAL

- Subject is unblinded

Subjects may voluntarily discontinue their participation in the study at any time without prejudice to further treatment.

7.8 Criteria for Permanent Discontinuation of Study Drug

Study drug treatment may be discontinued for the following reasons:

- if sponsor or regulatory authorities discontinue study
- if the PI believes that discontinuing treatment is in the best interest of the subject

7.9 Study Discontinuation

Synaptogenix has the right to discontinue this clinical study at any time. The PI has the right to discontinue participation in this clinical study at any time for any reason. Clinical study site discontinuation should only occur after mutual consultation between the PI and Synaptogenix.

Should the clinical study be discontinued prematurely, all subjects should be brought in for early termination procedures as outlined for the 30-day Follow-up visit. All clinical study materials should be returned to Synaptogenix or designee.

8 SAFETY MONITORING

A Data Safety Monitoring Board (DSMB) will provide consultation to Synaptogenix to assess the implementation and progress of study NTRP101-204 and will review accumulating trial data to monitor the safety of bryostatin administered to patients with AD. Safety data will be reviewed when 30 subjects have received four doses of study drug, followed by additional safety analyses when 60 subjects have received a similar number of doses. Medical decisions relevant to this study will be made by the Sponsor in consultation with the Primary Investigator, Medical Monitor and Statistician.

Prior to each safety review, a cut-off date for the data to be provided will be established by the Sponsor in consultation with the WCT Supporting Biostatistician. The format and content of data listings will be approved by the Supporting Biostatistician. Data reports will be provided as partially blinded displays (e.g., data is grouped by unblinded treatment using "Group A, B" to indicate treatment). The identity of each group will be available to the safety reviewer via the Supporting Statistician.

Data review documents, safety data tables and listings, will be provided to the DSMB at least 7 business days prior to scheduled reviews. Serious Adverse Events (SAEs) reported during the 7 days before the scheduled review and therefore not included in the provided documentation will be provided by the WCT Drug Safety Manager as soon as possible before the review date. The reviews of the safety data will be summarized for the overall subject group only and will not be separated by treatment groups.

CONFIDENTIAL

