Study Design This is a randomized double-blind placebo-controlled, Phase 2 study comparing bryostatin-1 to placebo for long-term efficacy in the treatment of moderately severe AD (Mini Mental State Examination, 2 nd edition scores of 10-18 at baseline) in the absence of memantine. Eligible subjects will receive 7 doses of bryostatin (i.v., 20µg) or matching placebo during the first 12 weeks. A second course of treatment consisting of 7 doses will begin 30 days after the final dose of the first treatment period. Cognitive tests will be assessed at intervals during the study and 30 days after the final dose of study drug. The primary endpoint is the total SIB score assessment obtained at Week 28, following completion of 2 courses of treatment. Randomization and Treatment Eligible subjects will be stratified based on baseline SIB total scores and will be randomized 1:1 to one of two treatment arms: 20µg bryostatin or placebo for twelve weeks, the first treatment period. The first two doses of study drug will be a loading dose 20% higher (i.e., 24µg) than the assigned dose and will be administered one week apart. Thereafter, the assigned dose of 20µg will commence with the third dose and be administered every other week. The second course of treatment will be identical to the first, beginning 30 days after		

CONFIDENTIAL

Name of Company: Synaptogenix, Inc.	Name of Study Medication: Bryostatin 1	Name of Active Ingredient: Bryostatin 1

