9.7 Safety Assessments

Unblinded summaries and listings of safety data will be provided to the Data Safety Monitoring Board, as described in Section 8. Analyses will be performed by an independent unblinded statistician so that study investigators and other sponsor personnel (and contractors) involved in study monitoring, data processing and other aspects of the study remain blinded.

CONFIDENTIAL

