8 DATA SAFETY MONITORING BOARD ANALYSIS

Safety data will be reviewed by Data Safety Monitoring Board (DSMB) when 30 subjects have received four doses of study drug, followed by additional safety analyses when 60 subjects have received a similar number of doses. Following tables and listings will be prepared for DSMB review:

Tables:

- Demographic data
- Disease history
- Medical history
- Summary of TEAEs
- Summary of TEAEs by relationship to clinical trial treatment
- Summary of Serious TEAEs
- Summary of Serious TEAEs by relationship to clinical trial treatment

QMD Ref: Worldwide-TMP-ST-005-7.0 Effective: 12Aug2019	Governing QMD: Worldwide-SOP-ST-001
Confidentiality Statement	
This document is the property of Worldwide Clinical Trials Inc. and may not be duplicated, copied, altered or removed from company without prior approval from Worldwide Quality Assurance or in compliance with Worldwide Standard Operating Procedures.	

Worldwide Clinical Trials Controlled Quality Management Document		
 WORLDWIDE CLINICAL TRIALS	Sponsor:	Synaptogenix, Inc.
	Protocol Number:	NTRP-101-204
STATISTICAL ANALYSIS PLAN. PHASE 2-3-4		

- Summary of Adverse Events of Special Interest (AESI)
- Summary of AESI by relationship to clinical trial treatment

Listings:

- Demographic data
- Disease history
- Medical history
- Pre-treatment AEs
- TEAEs
- Serious TEAEs
- TEAEs resulting in discontinuation of study treatment
- TEAE with fatal outcome

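### Protocol section 8 is inconsistent on whether the DSMB sees safety data by arm or pooled, and SAP section 8 does not settle it

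*Protocol*

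**What the plan says.** **Protocol section 8, second paragraph.** On the form of the reports: "Data reports will be provided as partially blinded displays". The example given is grouping by actual treatment under the codes A and B. On access to the code: "The identity of each group will be available to the safety reviewer via the Supporting Statistician".

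**Protocol section 8, third paragraph.** This paragraph deals with the documents sent to the board and when they are sent. It ends: "The reviews of the safety data will be summarized for the overall subject group only and will not be separated by treatment groups".

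**Protocol section 9.7.** "Unblinded summaries and listings of safety data will be provided to the Data Safety Monitoring Board, as described in Section 8". The analyses are to be done by an independent unblinded statistician, so that investigators, sponsor personnel and contractors involved in running the study stay blinded.

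**SAP section 8.** "Following tables and listings will be prepared for DSMB review". A list of tables and listings follows. It does not say whether they are split by arm. Where it mentions relationship to trial treatment, it means assessed causality, not allocation.

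**Timing and allocation.** "Safety data will be reviewed when 30 subjects have received four doses of study drug", and again at 60 subjects. Subjects are "randomized 1:1 to one of two treatment arms".

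**The concern.** In a placebo-controlled trial the board's main tool is the comparison between arms. Concurrent placebo data are what allow it to separate a drug effect from the background of events expected in people with moderately severe Alzheimer's disease. A statistician who prepares the DSMB package and follows the last sentence of section 8 as written would produce pooled tables. One who follows the preceding paragraph, or 9.7, would produce by-arm tables. Section 8 does not say which instruction governs, and it does not distinguish a closed report for the board from an open one for blinded staff. Only two data-triggered reviews are specified, so a package in the wrong format would use up one of two opportunities.

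**Working it through.** The plan states no figure on this point, so the check is a comparison of texts, followed by an illustration of what pooling hides.

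**Step 1. The statements side by side**

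| Place | What it implies for the DSMB tables |
|---|---|
| Protocol 8, second paragraph | By arm, coded A/B, code available to the safety reviewer |
| Protocol 8, closing sentence | Pooled, if it describes what the board receives |
| Protocol 9.7 | By arm and unblinded, with a cross-reference to section 8 |
| SAP 8 | Contents listed, layout not stated |
| SAP 6.3, 6.12, 6.12.1 (general conventions) | AE tables by treatment; listings sorted by treatment first |

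The first and third rows agree in substance but use different terms, partially blinded and unblinded. The second row conflicts with both if it describes the board's material. The cross-reference in 9.7 does not help, because it leads back to the section that contains the conflict.

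**Step 2. Can the SAP settle it?** Protocol section 9 and SAP section 6 give the SAP precedence over the analysis plans in the protocol. SAP 6.3 sets treatment columns for AEs and other safety data. SAP 6.12 presents safety by treatment received. SAP 6.12.1 asks for summaries by treatment group and overall, and most of the AE tables listed for the board in SAP 8 match its set. This is good evidence of intent. But SAP 8 neither repeats nor invokes these conventions, and they do not expressly displace a protocol sentence written about the safety reviews.

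**Step 3. What a pooled table hides (illustration only).** Inputs: treatment-related TEAE rates in study NTRP101-202 from Protocol 2.1.2.3, 16.7% on placebo (8 subjects) and 37.0% on 20 µg (17 subjects); review sizes of 30 and 60; 1:1 allocation, so about 15 and 30 per arm.

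- Pooled rate = (16.7% + 37.0%) / 2 = 26.85%.
- First review: 0.2685 × 30 = 8.1, about 8 subjects. Second review: 0.2685 × 60 = 16.1, about 16 subjects.

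Splits that give the same pooled count, with two-sided Fisher exact p-values:

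| Pooled 8/30 (15 per arm) | p | Pooled 16/60 (30 per arm) | p |
|---|---|---|---|
| 4 v 4 | 1.00 | 8 v 8 | 1.00 |
| 3 v 5 | 0.68 | 5 v 11 | 0.14 |
| 2 v 6 | 0.21 | 4 v 12 | 0.039 |
| 1 v 7 | 0.035 | 3 v 13 | 0.007 |
| 0 v 8 | 0.002 | 0 v 16 | <0.001 |

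The pooled count is the same in every row of a column, so pooled tables cannot distinguish balance from a marked imbalance.

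**Step 4. What by-arm tables would add at these sizes.** At the NTRP101-202 rates the expected counts are 15 × 0.167 = 2.5 v 15 × 0.370 = 5.6 at the first review, and 30 × 0.167 = 5.0 v 30 × 0.370 = 11.1 at the second. The normal-approximation power of a two-sided 5% comparison is about 23% and 42%. By-arm tables would show the direction and the individual cases by arm, but would often fall short of a formal signal.

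**The case against.** The strongest reply is grammatical. Section 8 has its own terms for what goes to the board: data reports, review documents, tables and listings. The closing sentence is instead about the reviews. It can be read as covering the write-up after each review, which has to be pooled if sponsor staff are to stay blinded as 9.7 requires. On that reading there is no conflict. The surrounding provisions support it: group codes, access to the code and an independent unblinded statistician would serve no purpose if the board saw only pooled data. The SAP's general conventions point the same way. A DSMB charter, which is not among the documents, may already fix the format.

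Most of this stands as evidence of intent, but it does not remove the ambiguity. The sentence names no recipient and no open report, and it sits at the end of the paragraph on material provided to the board.

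Two stronger readings are tempting and are not supported. A reader might infer that the plan decides to withhold arm-level safety data from the board; no such decision is documented, and 9.7 says the opposite. A reader might also infer that by-arm tables would reliably expose a harm that pooling conceals; at about 15 and 30 subjects per arm, Step 4 shows that they often would not.

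**Conclusion.** The inconsistency is real and is in the current protocol text. It is most likely one unreconciled sentence, not a choice to pool, and the alternative reading cannot be excluded. It should still be corrected. Followed literally, the sentence would deprive the board of the comparison between arms at both planned reviews, and SAP section 8 would not stop that from happening.

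The consequence is conditional on the literal reading being applied. It concerns safety monitoring only: the primary analysis, sample size, power and type I error are unaffected. The counts in the working assume the NTRP101-202 rates and equal arms, and the conclusion does not depend on them. No view is possible on what the board has actually received.

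**What to change.** 1. Replace the closing sentence of Protocol section 8 with wording such as: *Safety tables and listings for the DSMB are presented by treatment group, coded A and B, with the identity of each group available to the DSMB through the unblinded statistician. Only summaries of the review released to blinded sponsor or site staff are pooled across groups.*
2. Use one term for the DSMB package in Protocol section 8 and section 9.7, so that partially blinded and unblinded do not both describe it.
3. Add the words *by treatment group* to the list of DSMB tables in SAP section 8.
4. If a review has already taken place, confirm and file which format the board received.

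The cost is one replaced sentence, one aligned term and three words in the SAP. No dose, endpoint, sample size or alpha changes.
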